6.1. General

This study is a single blinded, randomised, crossover study divided into two parts; Part A and Part B. The study period consists of an information visit, an inclusion visit, six test visits and a termination visit.

- **Part A** evaluates two prototypes of intermittent catheters (Test product 2 and 3) compared to the standard catheter SpeediCath® Flex (Comparator).

In the investigation ten subjects will be included. The subjects will be catheterised once per visit. In part A (Test Visit 1-3) the subjects will be catheterised with the two test catheters and comparator in a randomised order. [REDACTED]

[REDACTED]. The order of the catheterisations will be randomised to prevent bias.

During the test visits the primary, secondary and explorative endpoints will be registered.

Subjects will be asked to participate in an interview in continuation of their last visit for part A (Test Visit 3) [REDACTED]. The interviews will be performed by a Coloplast representative asking questions related to their experience with the catheter. The subjects must sign a separate consent form for this purpose and can participate in the investigation without participating in the interview. In addition, subjects will be asked for consent to tape recording and filming during the interviews, but can participate in interviews without this.

In addition, a Coloplast representative will interview the Investigator and her representatives after LPO with questions related to their experience with the catheters.

The investigation is planned to be conducted in August 2018-Januar 2019. The visit window will be minimum five days between the visits (catheterisations), to ensure time for healing of any potential urethral trauma.

[REDACTED] However, the maximum time between visits should be adjusted to ensure the subject is terminated before LPO.

No biobank will be established for this investigation. All urine samples in the clinical investigation (for evaluating in- and exclusion criteria and for evaluating end points) will be destructed immediately after analysis.

6.1.1. End points and rationale for selection

End points	Type of assessment	Rationale for selection of end points
Primary end points	Urine flow rate	
Urine flow rate, measured by uroflowmetry, are an indicator for the test product performance.
 
Secondary end points	Post void residual urine	
Post void residual urine, measured with an ultrasound bladder scan are indicator for the test product performance.

	Amount of urine left in bladder (ml)	
Macroscopic haematuria is measured by assessing visible blood during catheterisation. This is an indicator for test product safety.

	
Did you experience visual blood during catheterisation (No/Yes) If yes, where was the blood (several answers accepted) (On the tip – at the eyelets – on the whole catheter – in the urine) 7 answer possibilities
	
Microscopic haematuria will be measured after each catheterisation using urine dipstick. This is an indicator for test product safety.

	
Negative - Neg - Non-hemolysed 10 Ery/µL (+/-) - Hemolysed 10 Ery/µL (+/-)
	
	
Positive - Non-hemolysed 80 Ery/µL (2+) - Hemolysed 25 Ery/µL (1+) - Hemolysed 80 Ery/µL (2+) - Hemolysed 200 Ery/µL (3+)
	
	
At least one positive response makes endpoint considered positive
	
This is an indicator for test product safety.

Explorative end points	Adverse events Overall discomfort during catheterisation	
Discomfort will be measured both during catheterisation, insertion, withdrawal and during post catheterisation

End points	Type of assessment	Rationale for selection of end points
Discomfort during insertion	
vertical line indicating how you experienced the overall catheterisation.
 
On a scale ranging from "no discomfort" to "worst possible discomfort" caused by the catheter, set a vertical line indicating how you experienced the insertion of the catheter.
 
On a scale ranging from "no discomfort" to "worst possible discomfort" caused by the catheter, set a vertical line indicating how you experienced the withdrawal of the catheter.
 
On a scale ranging from "no discomfort" to "worst possible discomfort" caused by the catheter, set a vertical line indicating how you experienced urination after the catheterisation.
 
How did you experience insertion of the catheter? (5 point scale: Very difficult – difficult – neither difficult nor easy – easy – very easy)
 
How did you experience withdrawal of the catheter? (5 point scale: Very difficult – difficult – neither difficult nor easy – easy – very easy)
 
Did you touch the coated part of the catheter during insertion? (Yes/No)
 
Did you experience urine running out of the catheters on the outside of the catheters? (Yes/No)
	
to investigate potential differences. Discomfort is measured by VAS-scale (10 cm horizontally line) – (assessed by subjects)
 
As the catheter design is relatively new, handling will be investigated and the information utilized in further development.

Discomfort during withdrawal		
Discomfort during urination post catheterisation		
Handling during insertion		
Handling during withdrawal		
Handling during insertion		
Handling during catheterisation		
Urine flow	
 - Micturition time (sec) - Flow time (sec) - Time to Qmax (sec) - Micturition volume (ml) 	
Urine flow, measured by uroflowmetry, are an indicator for the test product performance.
 

6.1.2. Discussion of clinical investigation design

This study is a single blinded, randomised, crossover study divided into two parts, with healthy subjects.

A cross-over design has been chosen over a parallel design due to minimisation of interpersonal variation. Only blinding of subjects is possible, since nurses will catheterise and since there is a visual difference in the products. A lower number of subjects are required with this study design as each subject act as his own control.

Healthy subjects have been chosen since discomfort must be evaluated by subjects with normal uréthral sensation. As this is an exploratory study no formal sample size calculation has been performed. However, it is assumed that ten subjects will be adequate for obtaining indications on performance and acceptance.

During the investigation, there must be a minimum of five days between each visit/catheterisation to allow potential micro trauma from the catheterisations to heal.

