6.6. Supplementary materials and equipment.....	24
6.7. Monitoring Plan	24
7. Statistical considerations.....	25
7.1. Statistical design, method and analytical procedures	25
7.2. Sample size.....	25
7.3. Level of significance and power.....	27
7.4. Drop-out	27
7.5. Pass/fail criteria	27

7.6. Interim analysis	27
7.7. Statistical reason for termination of investigation	27
7.8. Deviation(s) from statistical plan	27
8. Data management.....	27
8.1. Data review, database cleaning, and issuing and resolving data queries	27
8.2. Verification, validation and securing of electronic clinical data systems	27
8.3. Data retention	28
9. Amendments to the CIP.....	28
10. Clinical Investigation Plan deviations.....	28
11. Device Accountability.....	29
12. Statement of compliance.....	29
12.1. Ethics committee and regulatory authorities	30
12.2. Data protection	30
12.3. Indemnity	30
12.4. Financial conditions	30
13. Informed consent process	31
14. Adverse events, serious adverse events and device deficiencies	32
14.1. Adverse events	32
14.2. Device deficiency	32
14.3. Serious adverse events	32
14.4. Medical care of subjects	33
14.5. Reporting and timelines	33
15. Suspension or premature termination of the clinical investigation	34
16. Clinical investigation report.....	34
17. Publication policy	35
18. Bibliography	35

> SYNOPSIS OF THE CLINICAL INVESTIGATION

Objective

The primary objective of the investigation is to obtain indications that the intermittent catheters [REDACTED] can be used to void and empty the bladder

Primary end point and secondary end point(s)

The primary endpoint is: Urine flow rate

The secondary endpoints are: Post void residual urine, haematuria (macroscopic and microscopic) and adverse events.

Explorative endpoints are: Overall discomfort during catheterisation, discomfort during insertion, discomfort during withdrawal, discomfort during urination post catheterisation and handling during catheterisation.

Pass/fail criteria

No formal success criteria are applied in this explorative investigation. The investigation will provide valuable insight into both performance and acceptance of three new intermittent catheters [REDACTED]

Design of the investigation

The study is a single blinded, randomised, cross-over study [REDACTED]

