Subject is asked about symptoms for urinary tract infections (frequent urination, stinging or pain at urination) and use of analgetica up to 24 hours prior to the visit. In addition, a urine sample is made and microscopic haematuria, nitrite and leukocytes is measured before catheterisation to further ensure no symptoms of urinary tract infection or damage to the urinary tract system. If negative for these symptoms, use of analgetica and microscopic haematuria/nitrite/leukocytes, the subject will be catheterised with the randomised product and urine flow rate is measured. Hereafter the bladder is scanned for post void residual urine, by using a hand held bladderscanner, [REDACTED]. The subject is offered something to drink and after 1-2 hours a urine sample is made and microscopic haematuria measured. Subject and nurse register relevant answers in CRF, including possible adverse events. In addition, subject register the end points regarding discomfort (VAS-scale) and the nurse register the assessments in the CRF. Next visit is scheduled.

If subjects have agreed to participate in interviews, Test Visit 3 will be prolonged to include interview.

Test Visit (V5-V6) – approximately two hours

Subject is asked about symptoms for urinary tract infections (frequent urination, stinging or pain at urination) and use of analgetica up to 24 hours prior to the visit. In addition, a urine sample is made and microscopic haematuria, nitrite and leukocytes is measured before catheterisation to further ensure no symptoms of urinary

tract infection or damage to the urinary tract system. If negative for these symptoms, use of analgetica and microscopic haematuria/leukocytes/nitrite, the subject will be catheterised with the randomised product [REDACTED] [REDACTED] and urine flow rate is measured. Hereafter the bladder is scanned for post void residual urine, by using a hand held bladderscanner, [REDACTED]. The subject is offered something to drink and after 1-2 hours a urine sample is made and microscopic haematuria measured. Subject and nurse register relevant answers in CRF, including possible adverse events. In addition, subject register the end points regarding discomfort (VAS-scale) and the nurse register the assessments in the CRF. Next visit is scheduled.

If subjects have agreed to participate in interviews, Test Visit 6 will be prolonged to include interview. At the end of Test Visit 6 the termination page in CRF is completed by nurse.

Interview – plus one hour

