6.4.6. Blinding

During the investigation, the subject will be blinded with a curtain so he will not be able to see which catheter is used. The nurse is not blinded as it is not possible to blind the products due to visible differences. It is a disadvantage that it is not possible to blind the nurses as there could be some bias in their assessment of the products tested. However, it is the subject who assesses the secondary end points regarding discomfort (VAS) during catheterisation and micturition.

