12.4. Financial conditions

The investigation is initiated and sponsored by Coloplast A/S.

Coloplast pays the salary for the clinical staff in Denmark and for all investigation materials. The investigation expenses are expected to amount [REDACTED] per subject. The investigator is employed by Coloplast A/S, thus a Disclosure of Conflicts of Interests will be filled out before initiation of the investigation. An external nurse will be in-sourced to conduct the visits together with Coloplast personnel.

Subjects will be paid for their participation in the study and receives a gift voucher equivalent in value to [REDACTED] per visit. The gift is taxable (B-tax) and the subjects is responsible for reporting this.

13. Informed consent process

Written informed consent is obtained from all subjects participating in the investigation after thorough written and verbal information. The information is given by the investigator or his/her representative in the subjects' native non-technical language. Each subject will be fully informed about the aim of the investigation, procedures, potential risks or inconveniences and/or expected benefits and have a minimum of 24 hours before deciding on participation. The subjects will be informed that their participation is voluntary and that they may leave the investigation at any time, without this having any influence on their further treatment.

The informed consent signature form includes personally dated signatures of the subject and the Investigator or a representative hereof responsible for conducting the informed consent process. A copy will be provided to the subject.

If new information is to be given during the investigation, sponsor will inform the investigators, and the new information is given to the subjects by the investigator. If new information becomes available that can significantly affect a subject's future health and medical care that information will be provided to the subject in written form. Clinical Manager is responsible for writing the information and providing it to investigators that will further provide it to the subjects. If applicable, all affected subjects shall be asked to confirm their continuing informed consent in writing.

This procedure also applies to informed consent obtained from a subject's legal representative. The procedure cannot waive the subjects' legal rights.

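### Residual urine and microscopic haematuria could be read blind to product, but the plan says only subjects can be blinded, which leaves an avoidable risk of assessor bias

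*Combined protocol and SAP*

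**What the plan says.** Section 6.1.2 (Discussion of clinical investigation design) says: "Only blinding of subjects is possible, since nurses will catheterise and since there is a visual difference in the products". Section 6.4.6 (Blinding) gives the same reason: "The nurse is not blinded as it is not possible to blind the products due to visible differences". It concedes that "there could be some bias in their assessment of the products tested" and offers one protection: "However, it is the subject who assesses the secondary end points regarding discomfort (VAS) during catheterisation and micturition".

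The synopsis classifies the endpoints differently: "The secondary endpoints are: Post void residual urine, haematuria (macroscopic and microscopic) and adverse events". Both the synopsis and section 6.1.1 place discomfort among the explorative endpoints.

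Section 6.4.1 gives the order of events at a test visit. After catheterisation and flow measurement, "Hereafter the bladder is scanned for post void residual urine, by using a hand held bladderscanner". The subject is then offered a drink, and "after 1-2 hours a urine sample is made and microscopic haematuria measured". The flow-chart in section 6.4.4 lists both readings as made after catheterisation by the investigator, who may delegate to trained staff.

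On staffing, section 12.4 says: "An external nurse will be in-sourced to conduct the visits together with Coloplast personnel". The same section states that the investigator is a sponsor employee.

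**The concern.** The reason given for not blinding staff is that the nurse handles products that look different. That is sound for the person who inserts and withdraws the catheter. It does not explain why someone who only scans the bladder afterwards, or only reads a dipstick an hour or two later, must know which product was used. The plan does not address that possibility.

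Residual urine is the more important of the two readings. It is one of the two performance outcomes in the hypothesis (section 5.2), is analysed by a mixed model (section 7.1), and falls under the two-sided 5% level (section 7.3). A crossover removes differences between men. It does not remove an error that follows the product: if readings for one product are shifted by d ml, the whole of d enters that product's contrast with the comparator.

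The one safeguard in section 6.4.6, subject-rated discomfort, covers neither reading.

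**Working it through.** The plan states no figure on this point, so the check is mainly textual.

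**1. Which readings need sight of the product**

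| Reading | When it is made | Catheter must be seen? | Protected by the subject-rated VAS? |
|---|---|---|---|
| Residual urine (secondary) | After catheterisation and flow measurement (6.4.1) | No | No |
| Microscopic haematuria after catheterisation (secondary) | 1-2 hours later, new sample (6.4.1) | No | No |
| Macroscopic haematuria (secondary) | During catheterisation, including blood at tip and eyelets (6.1.1) | Yes | No |
| Discomfort (explorative) | Rated by the subject (6.1.1) | No | It is the VAS |

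The first two rows fall outside the reason given in sections 6.1.2 and 6.4.6. The third falls within it.

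**2. Who could read blind**

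Section 12.4 implies at least two staff roles, section 1.3 refers to study nurses in the plural, and section 6.4.4 allows delegation. Against that, section 6.4.5 has the investigator or a representative open the randomisation envelope at the inclusion visit, so that person may know the order before any test visit. An eligible reader must therefore not have catheterised, not have opened the envelope and not have been in the room. The documents do not say how many staff attend each visit.

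**3. Readings exposed, per endpoint**

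- Part A: 10 subjects x 3 visits = 30.
- Visits 1, 2, 3, 5 and 6 as named in section 7.1: 10 x 5 = 50.

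**4. Scale only, under assumed shifts**

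*Haematuria.* Section 6.1.1 puts the cut between haemolysed 10 (negative) and haemolysed 25 (positive). With ten men per product, one reading that crosses it changes that product's rate by 1/10 = 10 percentage points. This holds for any single misreading, random or not.

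*Residual urine.* Neither a standard deviation nor a bias size is given. Assume no true difference, n = 10 complete subjects, and a systematic shift of r standard deviations of the within-subject difference. The noncentrality is r x √10, and the two-sided 5% rejection rate is 1 - F(t; df, r√10) + F(-t; df, r√10), where F is the noncentral t distribution function and t is the 97.5% point of central t. Degrees of freedom were taken as 9 (paired, 10 - 1), 18 ((10 - 1) x (3 - 1)) and 16 (18 less 2 for visit).

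| Assumed r | r√10 | False-positive rate over df 9, 16, 18 |
|---|---|---|
| 0 | 0 | 5% |
| 0.10 | 0.32 | 6% |
| 0.25 | 0.79 | 11-12% |
| 0.50 | 1.58 | 29-32% |
| 0.75 | 2.37 | 56-61% |

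Blind reading aims to bring r back to 0. The table does not say which row applies to this trial.

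**The case against.** The case on the other side has weight in five respects.

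- **No bias is shown.** A reader might infer that the two endpoints are in fact biased. The documents do not support that: every rate above for a non-zero shift rests on an assumed shift.
- **Dependence on the operator is an assumption.** The text around the hand-held scanner is redacted (sections 6.4.1 and 6.6), and nothing says whether the dipstick is graded by eye or by machine. The flow-chart and section 6.7.1 allow for a print as source. A print would limit transcription error, though not an error in how the scan was taken.
- **Staffing is not settled.** A reader might infer from section 12.4 that a second, blind person is present at every visit and that the change needs nobody extra. The section does not say that both attend each visit or stay for the later sample, and one of them may have opened the envelope. Nor can the curtain in section 6.4.6 be counted as a screen for staff; it is described only as blocking the subject's view.
- **Haematuria can be protected only in part.** Visible blood is judged at catheterisation. If the rule in section 6.1.1 that one positive response makes the endpoint positive combines the two parts, the combined result stays partly unblinded.
- **The consequences are limited.** The study has ten subjects, is explorative and has no pass/fail criteria (sections 7.2 and 7.5). The primary endpoint comes from uroflowmetry and is not affected by this point. Haematuria is chiefly to be listed, although section 7.1 also mentions an odds ratio. Section 6.4.6 already discloses possible nurse bias.

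All five narrow the point. None supplies a reason why the scan and the later dipstick could not be read blind.

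**Conclusion.** The point holds as an avoidable risk of assessor bias in residual urine and in the microscopic part of haematuria. The stated ground for blinding subjects only does not reach these two readings, and the stated safeguard protects neither. That safeguard is also described wrongly, since section 6.4.6 calls discomfort secondary.

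The size of any bias cannot be derived from the documents. The conclusion rests on two assumptions: that the person measuring can influence the reading, and that at some visits at least a second trained person without knowledge of the allocation is available. The documents make the second plausible but do not state it.

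The gain is mainly for residual urine, which is in the hypothesis and is modelled. Macroscopic haematuria stays unblinded whatever is done. Blinding the scan protects the reading only; the drainage before it is still carried out by an unblinded nurse. In an explorative trial this is a worthwhile improvement rather than a fault that undermines the study.

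**What to change.** 1. In sections 6.1.2 and 6.4.6, limit the statement that blinding is impossible to the catheterising nurse and to assessments made during catheterisation.
2. In section 6.4.6, correct the description of discomfort from secondary to explorative, and state that subject rating does not protect residual urine or haematuria.
3. In section 6.4.1, where the external nurse and a sponsor staff member both attend, assign the bladder scan and the post-catheterisation dipstick to the trained delegate who did not catheterise, did not open the randomisation envelope and was not in the room during catheterisation.
4. Record both results on a separate CRF page that does not identify the product, and keep the scanner print where there is one.
5. Record who made each reading and whether it was blinded. Where only one person attends, or both know the allocation, flag the reading as unblinded rather than add staff.

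The cost is a rota constraint, with both people needed at the scan and the later sample, and one CRF page. Visits, procedures, sample size and the analysis model are unchanged.

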6.2. Investigational device and comparator(s)

During the study period, each subject will be exposed to one catheterisation per Test product 3, and [REDACTED] per Test product 2 and comparator. A total amount of ten of each test products and 20 comparator products are needed in the study. However, to ensure that the site has enough, more products than needed will be provided by Sponsor to the site. All products will be accounted for.

Each catheterisation lasts approximately 15 minutes totally.

Table 2: Overview of products needed in the investigation

Product	Description	Number of catheters needed/subject	Number of catheters needed in total
Test product 2	Prototype 2 of intermittent catheter	1	10
Test Product 3	Prototype 3 of intermittent catheter	1	10
Comparator	SpeediCath® Flex	1	10
[REDACTED]	[REDACTED]	[REDACTED]	[REDACTED]
[REDACTED]	[REDACTED]	[REDACTED]	[REDACTED]
[REDACTED]	[REDACTED]	[REDACTED]	[REDACTED]

Supplementing devices [REDACTED] instruments normally used for catheterisation (e.g. medical gloves, tray for urine collection) are supplied by Sponsor. Urine bags should not be connected to the catheters as this may affect the handling of the product. Neither may catheter accessories as gels be used on the catheter as this may affect the data.

